Product Description	
The Selective Cytopheretic Device (SCD) is comprised of tubing, connectors, and a synthetic membrane cartridge. The device is connected in series to a commercially available Continuous Renal Replacement Therapy (CRRT) device. Blood from the CRRT circuit is diverted after the CRRT hemofilter through to the extra capillary space (ECS) of the SCD. Blood circulates through this space and it is returned to the patient via the venous return line of the CRRT circuit. Regional citrate anticoagulation is used for the entire CRRT and SCD blood circuits.
 
The SCD █ is a synthetic membrane with the ability to bind activated leukocytes and when used in a continuous renal replacement extracorporeal circuit in the presence of regional citrate anticoagulation modulates inflammation.

Rationale	
Our primary hypothesis is that up to seven sequential 24-hour SCD treatments will improve survival in pediatric patients with Acute Kidney Injury (AKI) as compared to CRRT alone (standard of care). Further, SCD therapy will reduce the duration of maintenance dialysis secondary to AKI due to acute tubular necrosis (ATN). ATN is an acute reversible process and if not reversed in three months, it may not be reversed at all. [1, 2] Studies suggest that approximately 10-20% of AKI patients do not recover renal function [3, 4] and, therefore, require chronic dialysis.
 
Importantly, acute kidney injury is a highly lethal condition in critically ill patients. Despite improvements in acute medical care and advances in dialysis therapies, the mortality rate during the past four decades of this condition has not improved. Critically ill patients with AKI in hospital ICU settings have mortality rates of approximately 50%, including pediatric patients [5, 6, 7, 8, 9, 10, 11, 12]
 
AKI promotes a systemic inflammatory response syndrome (SIRS) which results in systemic microvascular damage and, if severe, multi-organ dysfunction. [13, 14] Activated circulating leukocytes play a central role in this process. [15] Leukocytes,

	especially neutrophils, are major contributors to the pathogenesis and progression of many inflammatory disorders, including SIRS, sepsis, ischemia reperfusion injury, and acute respiratory distress syndrome (ARDS). Many therapeutic approaches are under investigation to limit the activation and tissue accumulation of leukocytes at sites of inflammation to minimize tissue destruction and disease progression. [16, 17, 18]

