Primary Objective	To evaluate the safety of the SCD treatment up to seven consecutive 24 hour SCD treatments in the pediatric AKI population being treated with Continuous Renal Replacement Therapy (CVVH, CVVHD, or CVVHDF) with regional citrate anticoagulation.
Secondary Objective	To evaluate the effect of up to seven consecutive 24 hour SCD treatments on all cause mortality and dialysis dependency at day 28, and day 60 in the pediatric AKI population being treated with Continuous Renal Replacement Therapy (CVVH, CVVHD, or CVVHDF) with regional citrate anticoagulation. These outcomes will be compared to a historical data set.
Study Endpoints	In this Pilot study four domains of interest have been designated. The four domains are: 
 Patient Safety: Safety Endpoint Measures include adverse events, laboratory safety parameters, vital signs, EKG, ventilation status and hemodynamic variables. Clinical Efficacy: The Primary Clinical Efficacy Endpoint Measure is in-hospital; 28 and 60-day all-cause mortality. Time to renal recovery and necessity for chronic dialysis up to day 60 will also be determined. Additional efficacy endpoints include time to intensive care unit (ICU) discharge, and time to hospital discharge. Device Integrity and Performance: The Endpoint Measure is SCD use without failure. This measure will help assess the integrity and performance of the SCD device. SCD Mode of Action: Exploratory Endpoint Measures will include inflammatory cytokines, cell activation parameters and biomarkers at clinical sites with this capability.
Assessment of Device Integrity and Performance	Criteria for assessment of device integrity and performance include: 
 Significant Clotting within the Device as assessed by visual inspection. Evidence of leakage (i.e., cracking/breakage of a port, connector, hemofilter cartridge or tubing). Any unforeseen malfunction that results in the need for

	discontinuation.
Study Populations	Pediatric patients with a body weight (BW) greater than or equal to 15 kg receiving care in the Intensive Care Units of each participating hospital will be screened daily and identified for participation in the trial.
Study Design	This is an open-label, multi-center Pilot study.
Approximate Number of Subjects	Up to 30 patients will be enrolled in this study.
Approximate Number of Centers	Up to 10 Clinical Centers in the United States will participate in this study.

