	
17. Dry weight of <15 kg.18. Platelet count <15,000/mm³ at time of screening.19. Concurrent enrollment in another interventional clinical trial. Patients enrolled in clinical trials where only measurements and/or samples are taken (NO TEST DEVICE OR TEST DRUG USED) are allowed to participate.20. Use of any other Investigational drug or device within the previous 30 days.
Evaluation Plan	The primary evaluation of this study will be safety and all-cause mortality or dialysis dependency through 60 days post-enrollment. Additional endpoints will be time on CRRT, total ICU and hospital days. Mortality and dialysis dependency rates will be compared to historical controls.

LIST OF ABBREVIATIONS

[figure not shown]
AE	Adverse Event
AKI	Acute Kidney Injury
ARDS	Acute Respiratory Distress Syndrome
ARF	Acute Renal Failure
ATN	Acute Tubular Necrosis
BW	Body Weight
iCa	Ionized Calcium
CBC	Complete Blood Count
CRF	Case Report Form
CRRT	Continuous Renal Replacement Therapy
CTICU	Cardiothoracic Intensive Care Unit
CVVH	Continuous Veno-Venous Hemofiltration
CVVHD	Continuous Veno-Venous Hemodialysis
CVVHDF	Continuous Veno-Venous Hemodiafiltration
ECS	Extra Capillary Space
ICU	Intensive Care Unit
MICU	Medical Intensive Care Unit
nriCa	Non Recommended Ionized Calcium Range
ppCRRT	Prospective Pediatric CRRT Registry
PRISM	Pediatric Risk of Mortality
RAD	Renal Assist Device
riCa	Recommended Ionized Calcium Range
SAE	Serious Adverse Event
SCD	Selective Cytopheretic Device
SICU	Surgical Intensive Care Unit
SIRS	Systemic Inflammatory Response Syndrome
SOFA	Sequential Organ Failure Assessment
WBC	White Blood Cell
UADE	Unanticipated Adverse Device Effect

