3. PILOT STUDY (PROTOCOL SCD-PED-01) OBJECTIVES AND ENDPOINTS

3.1 PRIMARY OBJECTIVE

To evaluate the safety of the SCD treatment up to seven consecutive 24 hour SCD treatments compared to historic data on in-hospital mortality and on all cause mortality and dialysis dependency at day 28, and day 60 in the pediatric AKI population being treated with Continuous Renal Replacement Therapy (CVVH, CVVHD, or CVVHDF) with regional citrate anticoagulation.

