3.1.1 SECONDARY OBJECTIVE

To assess the effect of SCD treatment on various measures of pediatric patient clinical outcome and to evaluate the integrity of the SCD device and patient safety in SCD treatments from the time of initiation of therapy to as many as seven consecutive 24-hour SCD treatments.

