3.2 STUDY ENDPOINT

In this Pilot study four (4) domains of interest have been designated. The four (4) domains are:

1. Patient Safety: Safety Endpoint Measures include adverse events, laboratory safety parameters, vital signs, EKG, ventilation status and hemodynamic variables.
2. Clinical Efficacy: The Primary Clinical Efficacy Endpoint Measure is in-hospital; 28 and 60-day all-cause mortality. Time to renal recovery and necessity for chronic dialysis up to day 60 will also be

determined. Additional efficacy endpoints include time to intensive care unit (ICU) discharge, and time to hospital discharge.

3. Device Integrity and Performance: The Endpoint Measure is SCD use without failure. This measure will help assess the integrity and performance of the SCD device.
4. SCD Mode of Action: Exploratory Endpoint Measures will include inflammatory cytokines, cell activation parameters and biomarkers at clinical sites with this capability.

Endpoints are defined in **Appendix D**.

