Besides the test of the hypothesis the study is focused on observable, empirical and laboratory determinations of patient safety while on the SCD. Previous human trials have been conducted on the SCD device and the protocol contains a review of AE and SAE data from all SCD human studies and findings from those studies contributed to constructing the investigative safety profile. Safety endpoint measures specified in the protocol include adverse events, laboratory safety parameters, vital signs, ventilation status and hemodynamic variables. Device integrity and performance measurements are also defined as are circumstances which demand premature termination of SCD treatment.

Prolonged exposure to the SCD is anticipated to result in superior outcomes, although as noted above, this pilot study is not designed to assess for efficacy. However, we understand that a minimum amount of exposure to the SCD will be required for an appropriate safety analysis and for making any inference regarding efficacy. The ppCRRT experience demonstrated that the majority of patients (201/370) received CRRT for 1 to 7 days and exhibited 65% survival (Symons et al CJASN 2007 Table7). Assuming our trial includes patients with similar illness severity, we have established a 72 minimum number of hours a patient will be treated with the SCD to be included in the final outcome analysis.

This trial is an early safety efficacy study but is not powered for statistical significance. Insights into a comparison of historical controls matched to SCD treated patients will utilize the ppCRRT Registry to match for: etiology of AKI, co-morbidities, CRRT modality, dose and form of anticoagulant, adverse events. [10].

The ppCRRT Registry has data fields for the primary reason for CRRT, including AKI and its cause, as well as co-morbidities which will be matched for primary organ system involvement. The CRRT modality was evenly distributed between convective and diffusive modality, with 60% of the convective modalities provided as CVVH and 40% as CVVHDF. The anticoagulant protocol will be standardized with ACD-A/CaCl₂ and all centers used the same protocol in ppCRRT Registry as outlined in this study protocol. Thus, the ppCRRT Registry dataset will be able to be matched to our study patient cohort. Also as noted above, patients will be matched for age, size and PRISM II score.

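### The documents contradict each other on what is primary, and the primary efficacy measure is mortality at three unranked time points

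*Combined protocol and SAP*

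**What the plan says.** The synopsis states the Primary Objective as "To evaluate the safety of the SCD treatment up to seven consecutive 24 hour SCD treatments in the pediatric AKI population". Its Secondary Objective covers "all cause mortality and dialysis dependency at day 28, and day 60 in the pediatric AKI population", to be compared with a historical data set.

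Section 3.1 has a different primary objective: safety "compared to historic data on in-hospital mortality and on all cause mortality and dialysis dependency at day 28, and day 60". Section 3.1.1 then includes, as secondary, "to evaluate the integrity of the SCD device and patient safety in SCD treatments".

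The synopsis Evaluation Plan adds: "The primary evaluation of this study will be safety and all-cause mortality or dialysis dependency through 60 days post-enrollment". Its closing sentence says that mortality and dialysis dependency rates will be compared with historical controls.

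On efficacy, the synopsis and Section 3.2 say: "The Primary Clinical Efficacy Endpoint Measure is in-hospital; 28 and 60-day all-cause mortality". Appendix D, to which Section 3.2 refers for definitions, repeats the three time points without ranking them. The Rationale in the synopsis says: "Our primary hypothesis is that up to seven sequential 24-hour SCD treatments will improve survival in pediatric patients with Acute Kidney Injury". Section 1.1 says much the same, and neither gives a time point.

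Section 11 says that "this pilot study is not designed to assess for efficacy" and that the trial is not powered for statistical significance. It also says that the results will inform the design of a pivotal study. Section 10 plans an efficacy evaluation against historical controls after 16 patients, without naming the outcome.

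**The concern.** A reader of the final report should be able to tell from the protocol which result was meant to carry most weight. Here that depends on the page. By the synopsis objective it is safety. By Section 3.1 it is safety together with mortality and dialysis dependency against history. By the Evaluation Plan it is safety with death or dialysis dependency to day 60. Among the mortality results, any of three could be presented as the primary efficacy finding.

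In a trial without a decision rule, the label of primary is the main guide to which result to weigh. If it is loose, the historical comparison can be reported with emphasis on whichever outcome looks best, and that comparison is to feed into a pivotal trial. Section 2.5 shows that the choice can matter for this device. At the SCD-003 interim analysis, 60-day mortality was 39% (27/69) with the device and 36% (21/59) without it. In a subgroup defined by calcium control, death or dialysis dependency was 3/19 against 15/27. The endpoint and the subset both changed between those two results, and so did the apparent conclusion.

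**Working it through.** **Step 1: the statements side by side.**

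| Place | Safety | Mortality and dialysis dependency v history |
|---|---|---|
| Synopsis, Primary and Secondary Objective | Primary | Secondary; days 28 and 60 |
| Section 3.1 | Primary | Within the primary objective; in-hospital mortality added |
| Section 3.1.1 | Listed again as secondary | Clinical outcome measures, secondary |
| Synopsis, Evaluation Plan | Primary evaluation | Death or dialysis dependency to day 60, also primary evaluation |
| Synopsis endpoints, Section 3.2, Appendix D | One of four domains | Mortality in hospital, at day 28 and at day 60; no order |
| Synopsis Rationale, Section 1.1 | Not mentioned | Primary hypothesis is survival; no time point |

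The first two rows cannot both hold: the historical comparison is either secondary or part of the primary objective. Sections 10 and 11 do not settle it. They give no lead outcome, test, order of endpoints or success criterion.

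**Step 2: how much an open choice among the three mortality results could matter.** The plan has no power, alpha or decision figure to reproduce, so this is an illustration.

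From the documents: n = 16 (Section 10) and n = 30 (the maximum in Section 5.1).

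Assumed:
- True mortality equals history: p = 0.30 at day 28, 0.33 in hospital, 0.36 at day 60.
- History is known without error.
- Day-28 deaths are a subset of in-hospital deaths, which are a subset of day-60 deaths.
- A result looks favourable if it lies 15 or more points below history.

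A result is favourable if the number of deaths X ≤ n(p − 0.15), rounded down. X is binomial(n, p).

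| | n=16: cut-off | Chance | n=30: cut-off | Chance |
|---|---|---|---|---|
| Day 28 | 16 × 0.15 = 2.4, so ≤ 2 | 9.94% | 30 × 0.15 = 4.5, so ≤ 4 | 3.02% |
| In hospital | 16 × 0.18 = 2.88, so ≤ 2 | 6.26% | 30 × 0.18 = 5.4, so ≤ 5 | 3.85% |
| Day 60 | 16 × 0.21 = 3.36, so ≤ 3 | 11.70% | 30 × 0.21 = 6.3, so ≤ 6 | 4.67% |
| At least one | | 14.51% | | 6.11% |

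The last row sums the multinomial probabilities with cells 0.30 (dead by day 28), 0.03 (later in-hospital death), 0.03 (other death by day 60) and 0.64 (alive at day 60).

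Excess over day 60 alone: 14.51 − 11.70 = 2.81 points at n=16, and 6.11 − 4.67 = 1.44 points at n=30.

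**Step 3: a second set of assumptions.** Take exact one-sided binomial tests at an assumed 0.05 against a fixed historical rate. Let day-60 mortality be 35% to 50%, with 60% to 90% of those deaths by day 28 and 95% of them in hospital. Simulation gives 4.1% to 7.6% for at least one of the three, against 2.3% to 5.1% for day 60 alone. Treating the three as independent would give 1 − 0.95³ = 14.3%, which overstates the problem because largely the same deaths are counted each time.

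**The case against.** The strongest reply is that this is a pilot, and Section 11 says so. There is no alpha, test or pass/fail rule, and only basic statistics are planned. Multiplicity in the formal sense therefore does not arise, and the historical comparison is already close to descriptive. That stands, and it limits the point to clarity and emphasis. It does not remove the point: Section 10 still plans an efficacy evaluation, Section 3.1 still makes the historical comparison primary, and the text that disclaims efficacy does not say which objective governs.

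Several stronger readings are tempting, and the documents do not support them.

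- A reader might count three primary objectives. Only two statements carry that title, in the synopsis and in Section 3.1. The third is called a primary evaluation. All three include safety and differ on what stands beside it.
- A reader might infer a co-primary composite of death or dialysis dependency. The Evaluation Plan can be read that way, but its closing sentence speaks of separate rates, and Appendix D defines no composite.
- A reader might infer that the trial's verdict can be picked after the data are seen. No rule gives a verdict, and nothing in the text speaks to intent.
- A reader might say that in-hospital mortality will be incomplete because children remain in hospital at day 60. Follow-up does end then, but no length-of-stay figure is given, so this is plausible and no more.

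Most of the 11.7% at n=16 is small-sample noise, which naming one endpoint would not remove.

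**Conclusion.** The contradiction is real and is not resolved anywhere in the documents. The synopsis and Section 3.1 disagree on whether the historical comparison is primary. Section 3.1.1 repeats safety as secondary, the Evaluation Plan gives a further version, and the three mortality time points are unranked.

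The consequence is scope for selective emphasis, and it is modest: about 3 percentage points at n=16 and 1.5 at n=30 for the three mortality results. Those figures rest on the assumed rates, the 15-point threshold, nested deaths and a fixed historical rate. They are not the trial's type I error. The case for correction rests mainly on the contradiction itself, which needs repair whatever the error rate. It should be corrected, but it does not invalidate the design.

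**What to change.** - **Objective.** Keep one primary objective, safety, as in the synopsis Primary Objective; this agrees with Section 11. Use identical wording in the synopsis, the Evaluation Plan and Section 3.1, and remove patient safety from Section 3.1.1.
- **Lead efficacy measure.** Name one with a fixed horizon. Day-60 all-cause mortality fits, because follow-up ends then and status can be ascertained for every patient who is not lost or withdrawn. That is not a guarantee of completeness: consent withdrawal stops study activity (Section 7.4), and six of 65 SCD-003 controls lacked day-60 status (Table 5).
- **Other outcomes.** Label day-28 mortality, in-hospital mortality (truncated at day 60), dialysis dependency and any composite as secondary in the synopsis endpoints, Section 3.2 and Appendix D. If a composite is meant in the Evaluation Plan, define it; if not, reword the sentence as separate rates.
- **Status of the comparison.** State that all historical comparisons are descriptive, and align the primary hypothesis in the synopsis Rationale and Section 1.1 with that.
- **Appendix D.** Correct the definition of dialysis dependency. As written it describes a patient who is not receiving renal replacement therapy, which is the opposite state.

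The cost is wording: no added patients, visits or data. The sponsor commits in advance to one lead efficacy result.

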3.1.1 SECONDARY OBJECTIVE

To assess the effect of SCD treatment on various measures of pediatric patient clinical outcome and to evaluate the integrity of the SCD device and patient safety in SCD treatments from the time of initiation of therapy to as many as seven consecutive 24-hour SCD treatments.

3.2 STUDY ENDPOINT

In this Pilot study four (4) domains of interest have been designated. The four (4) domains are:

1. Patient Safety: Safety Endpoint Measures include adverse events, laboratory safety parameters, vital signs, EKG, ventilation status and hemodynamic variables.
2. Clinical Efficacy: The Primary Clinical Efficacy Endpoint Measure is in-hospital; 28 and 60-day all-cause mortality. Time to renal recovery and necessity for chronic dialysis up to day 60 will also be

determined. Additional efficacy endpoints include time to intensive care unit (ICU) discharge, and time to hospital discharge.

3. Device Integrity and Performance: The Endpoint Measure is SCD use without failure. This measure will help assess the integrity and performance of the SCD device.
4. SCD Mode of Action: Exploratory Endpoint Measures will include inflammatory cytokines, cell activation parameters and biomarkers at clinical sites with this capability.

Endpoints are defined in **Appendix D**.

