Duration of Subject Participation	Each patient will be followed for 60 days following enrollment.
Inclusion Criteria	
 1. A patient, or legal representative, has signed a written informed consent form. 2. Must be receiving medical care in an intensive care unit (e.g., PICU, MICU, SICU, CTICU, Trauma). 3. Age less than 22 years. 4. Females of child bearing potential who are not pregnant (confirmed by a negative serum pregnancy test) and not lactating if recently post-partum. 5. Intent to deliver full supportive care through aggressive management utilizing all available therapies for a minimum of 96 hours. 6. Clinical diagnosis of AKI due to etiologies requiring CRRT (see Appendix B). AKI is defined as acute kidney injury with any one of the following: 
 • Increase in SCr by ≥ 0.3 mg/dL (≥ 26.5 $\mu\text{mol/L}$) within 48 hours or; • Increase in SCr to ≥ 1.5 times baseline, which is known or presumed to have occurred within the prior 7 days or; • Urine volume $<0.5\text{ml/kg/h}$ for 6 hours 7. At least one non-renal organ failure (defined as receiving mechanical ventilation or at least one vasoactive medication to treat hypotension) OR presence (proven or suspected) of sepsis. (Appendix C).

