1.1 RATIONALE FOR THERAPY

Our primary hypothesis is that up to seven sequential 24-hour SCD treatments will improve survival in patients with Acute Kidney Injury (AKI) as compared to CRRT alone (standard of care). Further, SCD therapy will reduce the duration of maintenance dialysis secondary to AKI due to acute tubular necrosis (ATN). ATN is an acute reversible process and if not reversed in three months, it may not be reversed at all. [1, 2] Studies suggest that approximately 10-20% of AKI patients do not recover renal function [3, 4] and, therefore, require chronic dialysis.

Importantly, acute kidney injury is a highly lethal condition in critically ill patients. Despite improvements in acute medical care and advances in dialysis therapies, the mortality rate during the past four decades of this condition has not improved. Critically ill patients with AKI in hospital

ICU settings have mortality rates of up to 50%, including pediatric patients [5, 6, 7, 8, 9, 10, 11, 12]

AKI promotes a systemic inflammatory response syndrome (SIRS) which results in systemic microvascular damage and, if severe, multi-organ dysfunction. [13, 14] Activated circulating leukocytes play a central role in this process. [15] Leukocytes, especially neutrophils, are major contributors to the pathogenesis and progression of many inflammatory disorders, including SIRS, sepsis, ischemia reperfusion injury, and acute respiratory distress syndrome (ARDS). Many therapeutic approaches are under investigation to limit the activation and tissue accumulation of leukocytes at sites of inflammation to minimize tissue destruction and disease progression. [16, 17, 18] Preclinical studies utilizing a porcine model of septic shock have demonstrated that SCD therapy immunomodulates activated circulating leukocytes. This effect is associated with improvement of multiorgan dysfunction. [19]

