6.5.3 DAY 60 POST ENROLLMENT

This visit may be done via telephone call or office visit. Please record the following information on day 60 (+7 days) following enrollment:

- Presence / dates of mechanical ventilation (since last visit)
- Presence / dates of renal replacement therapy (since last visit)
- ICU discharge date
- Hospital discharge date
- Serious Adverse events (since last visit)
- Serum creatinine (if an office visit takes place)

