9.7.2. ENROLLMENT PERIOD THROUGH END OF STUDY

All adverse events that occur from the time of enrollment will be recorded as follows:

- Serious Adverse Events (identified in **Section 9.2**) will be recorded until Day 60 after enrollment, death, or patient withdrawal of study consent, whichever occurs first.
- Non-serious adverse events will be recorded until end of study follow-up period after enrollment, death, patient withdrawal of study consent or until hospital discharge, whichever occurs first.

Any serious adverse event (regardless of relationship to the treatment) occurring from the time of enrollment through end of study must be reported to CytoPherx Inc, or designee, within 24 hours of knowledge of the event.

Each clinical trial site will be supplied with written SAE reporting

instructions, SAE reporting forms and contact information for reporting of serious adverse events.

For any AE that is ongoing at the time of the initial report, periodic follow-up information will be required until the adverse event is resolved or the patient is no longer in the study, whichever occurs first.

The Investigator is responsible for all adverse events reporting to the Institutional Review Board (IRB) according to the requirements of the IRB and for providing clinical trial monitors with all medical records needed to source-verify the adverse events.

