APPENDIX D – ENDPOINT DEFINITIONS

ALL-CAUSE MORTALITY:

All cause mortality is defined as in-hospital, 28-day and 60-day all cause mortality.

DIALYSIS DEPENDANCY AT DAY 60:

Dialysis dependency at day 60 is defined as patient not receiving any form of intermittent or continuous renal replacement therapy at or within 3 days of 60 days post enrollment in the study with no plans for additional intermittent or continuous renal replacement therapy.

PATIENT SAFETY:

Adverse events, laboratory safety parameters, vital signs, EKG, ventilation status and hemodynamic variables.

DURATION OF RENAL SUPPORT:

The duration of renal support will be defined as the numbers of days from the initiation of renal replacement therapy (start of observation period) to final dialysis treatment. Duration of renal support will be censored if the patient is still dialysis dependent at the time of death or are dependent at day 60.

RECOVERY OF RENAL FUNCTION:

Recovery of renal function will be defined as lack of need for continuous dialysis support on day 28, and will be classified as yes or no at day 28. Subjects who were alive at day 28 will be included in the analysis. Patients who remain dialysis dependent at study completion (day 60) or time of death will be categorized as having no recovery of renal function.

ASSESSMENT OF SCD █ INTEGRITY AND PERFORMANCE:

The SCD █ will be evaluated for the presence of clotting, leaking or any other malfunction.

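### In-hospital mortality has no day limit while follow-up ends at day 60: it cannot be completed for children still inpatients then, and its historic comparison may have unequal horizons

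*Combined protocol and SAP*

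**What the plan says.** Section 3.2 (repeated in the synopsis) names three mortality measures together: "The Primary Clinical Efficacy Endpoint Measure is in-hospital; 28 and 60-day all-cause mortality". It refers the reader to Appendix D for definitions, but Appendix D only lists the names again: "All cause mortality is defined as in-hospital, 28-day and 60-day all cause mortality". The first of the three carries no day.

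Section 3.1 treats in-hospital mortality as separate from the dated measures and sets it against an external source: "compared to historic data on in-hospital mortality and on all cause mortality and dialysis dependency at day 28, and day 60".

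Data collection does have an end. The synopsis says "Each patient will be followed for 60 days following enrollment". Section 9.7.2 says serious adverse events, which include deaths, "will be recorded until Day 60 after enrollment, death, or patient withdrawal of study consent, whichever occurs first". The last contact is in Section 6.5.3: "Please record the following information on day 60 (+7 days) following enrollment". ICU and hospital discharge dates are collected at that contact, and Appendix H lists discharge information at both day 28 and day 60.

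On dialysis, the synopsis and Section 3.2 say "Time to renal recovery and necessity for chronic dialysis up to day 60 will also be determined", while Section 1.1 says "ATN is an acute reversible process and if not reversed in three months, it may not be reversed at all".

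**The concern.** In its ordinary sense, in-hospital mortality means death before discharge, whenever that occurs. A study that stops at day 60 cannot complete that measure for a child who is still an inpatient on that day. The plan neither follows such children to discharge nor says how they are to be classified.

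This matters because there is no concurrent control arm. In a randomised comparison both arms would be cut at the same day. Here the cut is stated for the treated children only, and Section 11 lists the factors on which registry patients will be matched without giving a common outcome horizon. Any difference in horizon passes directly into the comparison.

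A smaller question of wording arises for dialysis. The endpoint speaks of chronic need but is read about a month before the protocol's own three-month mark for reversibility.

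**Working it through.** The documents give no sample-size derivation, power or effect size, so there is no planned figure to reproduce. The check sets the horizons side by side and then sizes the gap under stated assumptions.

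**1. Horizons**

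| Item | Closing day | Source |
|---|---|---|
| 28-day mortality | 28 | 3.2, Appendix D |
| 60-day mortality | 60 | 3.2, Appendix D |
| In-hospital mortality | none given | 3.1, 3.2, Appendix D |
| Capture of deaths as serious adverse events | 60 | 9.7.2 |
| Last contact | 60 to 67 (60 + 7) | 6.5.3, Appendix H |
| Historic in-hospital mortality | not stated | 3.1, 11 |

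The two dated measures close within follow-up. The undated one need not.

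**2. Direction**

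Let M be mortality before discharge with no day limit, M60 the part that occurs by day 60, and L the part after day 60, so M = M60 + L. The trial can observe only M60. If the historic figure is M and the device has no effect, the expected difference (trial minus historic) is M60 − M = −L, which is zero or negative and so favours the device. If the historic figure is also cut at day 60, the expected difference is zero.

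**3. Size**

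Inputs from the documents:
- N = 30, the maximum enrolment (synopsis, 5.1).
- N = 16, the number at which Section 10 places the efficacy evaluation.
- 65% survival among registry patients treated for 1 to 7 days (Section 11). No horizon is given for it, so it serves here only as a rough share alive at day 60.

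Assumptions, with no figure in the documents:
- h, the share of survivors still inpatients at day 60: 5% to 20%.
- d, the share of those who later die in hospital: 10% to 30%.

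Formulas: survivors S = 0.65 × N; missed deaths = S × h × d; effect in points = 100 × missed deaths / N.

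- S = 0.65 × 30 = 19.5, or 0.65 × 16 = 10.4.
- Low end, N=30: 19.5 × 0.05 × 0.10 = 0.10 deaths; 0.0975 / 30 = 0.3 points.
- High end, N=30: 19.5 × 0.20 × 0.30 = 1.17 deaths; 1.17 / 30 = 3.9 points.
- N=16: 0.05 to 0.62 deaths, which is the same 0.3 to 3.9 points.
- Chance of at least one missed death, 1 − (1 − hd)^S with S rounded to 20 or 10: 10% to 71% at N=30, and 5% to 46% at N=16.
- One patient: 1/30 = 3.3 points; 1/16 = 6.3 points.

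**4. Dialysis wording**

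Taking three months as about 90 days, day 60 falls 90 − 60 = 30 days short, and the latest contact 90 − 67 = 23 days short. Appendix D puts a patient on dialysis at day 60 in the non-recovery category, yet censors that patient's duration of renal support at the same day. Censoring leaves the later course open, whereas the category closes it.

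**The case against.** **A reader might infer that late in-hospital deaths are scored as survivals.** The documents do not say so. A child who dies on day 75 is correctly alive for 60-day mortality. For in-hospital mortality the handling is simply not specified. The defect is an outcome that cannot be determined, not a stated rule that miscounts it.

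**A reader might infer that the comparison is biased as it stands.** That needs a historic figure running to discharge, and the documents do not give the registry's outcome horizon. The synopsis names only day 28 and day 60 for its historic comparison, and its evaluation plan runs through 60 days. Only Section 3.1 adds in-hospital mortality. The bias is therefore conditional. Section 3.1 nevertheless commits to the comparison, and nothing in the plan ensures equal horizons.

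**The rates used for size are assumed.** This stands. The documents say nothing about length of stay, so the range gives scale only.

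**The study is a pilot, directed first at safety and not powered for efficacy.** This limits the weight of the point. It does not excuse an undated measure listed among the primary clinical efficacy measures, since Section 11 says the results will help guide a pivotal design.

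**The dialysis point is mostly wording.** This stands too. Appendix D already defines its endpoint at day 60, and the phrase in Section 3.2 is itself limited to day 60. A reader might be tempted to set the 4/16 (25%) of surviving controls on dialysis at day 60 in the earlier pivotal trial's calcium-range subgroup against the 10-20% non-recovery cited in Section 1.1, and call the excess reversible. The denominators differ: over all patients in that arm the figure is 4/27 = 14.8%, inside 10-20%. The treated arm had 0/16, and all survivors in the earlier US pilot were off dialysis at day 60. No excess can be estimated from these data.

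**Conclusion.** The point holds in a limited form. One of the three primary clinical efficacy mortality measures is undated, is compared with historic data, and cannot be completed for a child still in hospital at day 60. The 28- and 60-day measures are sound in this respect.

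If the historic figure runs to discharge, the comparison favours the device by about 0.3 to 3.9 percentage points. This rests on the assumed inpatient and late-death rates and on 65% alive at day 60. If the historic figure is cut at day 60, there is no bias of this kind. In either case a single unclassified child moves the rate by 3.3 points at N=30 or 6.3 at N=16.

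The dialysis issue is secondary. Section 1.1 says only that injury not reversed by three months may not reverse; it does not say that dialysis at day 60 is generally reversible. The words chronic and non-recovery claim more than a 60-day observation can show, but no passage claims permanent kidney loss.

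**What to change.** 1. In the synopsis, 3.1, 3.2 and Appendix D, define the measure as in-hospital death by day 60.
2. Apply the same day-60 cut to the matched registry records, and say so in Section 11.
3. Report beside it the number of children still hospitalised at day 60. The discharge information already collected is enough for this.
4. Replace the chronic-dialysis phrase in the synopsis and Section 3.2 with Appendix D's term, dialysis dependency at day 60, and word the non-recovery category as no recovery by day 60. When doing so, correct the definition under that term: it currently describes a patient who is not receiving renal replacement therapy, and its 3-day window differs from the +7-day visit window.

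**Cost.** These are wording changes and one date cut, with no new visit. The endpoint becomes narrower: in-hospital death by day 60 is contained within 60-day mortality and differs from it only by deaths after discharge. Item 2 depends on the registry holding dates of death and discharge, which the documents do not confirm. If it does not, the report should state that the horizons may differ.

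**Optional.** One check at about day 90, from the chart or by telephone, for the few children still in hospital or on dialysis at day 60. This would need consent wording and is not required for items 1 to 4.
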